# Tx goal< A1c <9 AND [FBG ≤130(150) OR PPBG ≤180(200)] → Use dosing recommendations for 6≤ A1c ≤Tx goal

# 9≤ A1c ≤14 AND FBG >130(150) OR PPBG >180(200)

- 1. Metformin without problems, adherent
  - a. Metformin 850 mg  $\rightarrow$  metformin 1700 mg + glibenclamide 2.5 mg
  - b. Metformin 1700 mg  $\rightarrow$  metformin 1700 mg + glibenclamide 2.5 mg
  - c. Metformin 2550 mg  $\rightarrow$  metformin 2550 mg + glibenclamide 2.5 mg
- 2. Metformin without problems, nonadherent
  - a. Metformin 850 mg  $\rightarrow$  metformin 1700 mg
  - b. Metformin 1700 mg  $\rightarrow$  metformin 1700 mg
  - c. Metformin 2550 mg  $\rightarrow$  metformin 2550 mg
- 3. Metformin with problems, adherent
  - a. Metformin 850 mg, agrees to take metformin  $\rightarrow$  metformin 850 mg + glibenclamide 2.5 mg
  - b. Metformin 850 mg, refuses to take metformin  $\rightarrow$  glibenclamide 2.5 mg
  - c. Metformin 1700 mg  $\rightarrow$  metformin 850 mg + glibenclamide 2.5 mg
  - d. Metformin 2550 mg → metformin 1700 mg + glibenclamide 2.5 mg
- 4. Metformin with problems, nonadherent  $\rightarrow$  same as #3
- 5. Glibenclamide without problems, no previous problems with metformin, adherent
- a. All doses  $\rightarrow$  metformin 1700 mg +glibenclamide current dose
- 6. Glibenclamide without problems, no previous problems with metformin, nonadherent
  - a. All doses  $\rightarrow$  metformin 1700 mg + glibenclamide 2.5 mg
- 7. Glibenclamide without problems, previous problems with metformin, adherent
  - a. Agrees to take metformin  $\rightarrow$  metformin 850 mg + glibenclamide current dose
    - b. Refuses to take metformin
      - i. Glibenclamide 2.5 mg  $\rightarrow$  glibenclamide 5 mg
      - ii. Glibenclamide 5 mg  $\rightarrow$  glibenclamide 10 mg
      - iii. Glibenclamide 10 mg  $\rightarrow$  glibenclamide 10 mg
- 8. Glibenclamide without problems, previous problems with metformin, nonadherent
  - a. Agrees to take metformin
    - i. Glibenclamide 2.5-5 mg → metformin 850 mg + glibenclamide 2.5 mg
    - ii. Glibenclamide 10 mg  $\rightarrow$  metformin 850 mg + glibenclamide 5 mg
  - b. Refuses to take metform in  $\rightarrow$  continue current glibenclamide dose
- 9. Glibenclamide with hypoglycemia or hypoglycemia symptoms, no previous problems with metformin, adherent
  - a. Glibenclamide 2.5 mg  $\rightarrow$  metformin 1700 mg
  - b. Glibenclamide 5 mg  $\rightarrow$  metformin 1700 mg + glibenclamide 2.5 mg
  - c. Glibenclamide 10 mg  $\rightarrow$  metformin 1700 mg + glibenclamide 5 mg
- 10. Glibenclamide with hypoglycemia or hypoglycemia symptoms, no previous problems with metformin, nonadherent → same as #9
- 11. Glibenclamide with hypoglycemia or hypoglycemia symptoms, previous problems with metformin, adherent
  - a. Agrees to take metformin
    - i. Glibenclamide 2.5 mg  $\rightarrow$  metformin 850 mg
    - ii. Glibenclamide 5 mg  $\rightarrow$  metformin 850 mg + glibenclamide 2.5 mg
    - iii. Glibenclamide 10 mg  $\rightarrow$  metformin 850 mg + glibenclamide 5 mg
  - b. Refuses to take metformin

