  - c. Metformin 1700-2550 mg + glibenclamide 5 mg  $\rightarrow$  metformin 1700 mg + glibenclamide 2.5 mg
  - d. Metformin 1700-2550 mg + glibenclamide 10 mg  $\rightarrow$  metformin 1700 mg + glibenclamide 5 mg
- 14. Metformin and glibenclamide without problems, nonadherent, took glibenclamide yesterday  $\rightarrow$  same as #13
- 15. Metformin and glibenclamide without problems, adherent, did not take glibenclamide yesterday  $\rightarrow$  metformin 1700 mg

<sup>18 Numbers in parentheses refer to the relevant measurements for patients who have relaxed glycemic goals (A1c ≤8, FBG 90-150, PPBG <200)

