#### 5≤ A1c <6

- 1. Metformin without problems, adherent
  - a. Metformin 850 mg  $\rightarrow$  metformin 850 mg
  - b. Metformin 1700 mg  $\rightarrow$  metformin 1700 mg
  - c. Metformin 2550 mg  $\rightarrow$  metformin 1700 mg
- 2. Metformin without problems, nonadherent  $\rightarrow$  stop medications, recheck A1c in 3 months
- 3. Metformin with problems, adherent
  - a. Metformin 850 mg, refuses to take metformin → stop medications, recheck A1c in 3 months
  - b. Metformin 850 mg, agrees to take metformin  $\rightarrow$  metformin 850 mg
  - c. Metformin 1700 mg  $\rightarrow$  metformin 850 mg
  - d. Metformin 2550 mg  $\rightarrow$  metformin 1700 mg
- 4. Metformin with problems, nonadherent  $\rightarrow$  stop medications, recheck A1c in 3 months
- 5. Glibenclamide without problems, no previous problems with metformin, adherent
- a. All doses  $\rightarrow$  metformin 1700 mg
- Glibenclamide without problems, no previous problems with metformin, nonadherent → stop medications, recheck A1c in 3 months
- 7. Glibenclamide without problems, previous problems with metformin, adherent
  - a. All doses, agrees to take metformin  $\rightarrow$  metformin 850 mg
  - b. All doses, refuses to take metformin  $\rightarrow$  stop medications, recheck A1c in 3 months
- 8. Glibenclamide without problems, previous problems with metformin, nonadherent  $\rightarrow$  stop medications, recheck A1c in 3 months
- Glibenclamide with hypoglycemia or hypoglycemia symptoms, no previous problems with metformin, adherent → same as #5
- 10. Glibenclamide with hypoglycemia or hypoglycemia symptoms, no previous problems with metformin, nonadherent → stop medications, recheck A1c in 3 months
- 11. Glibenclamide with hypoglycemia or hypoglycemia symptoms, previous problems with metformin, adherent → same as #7
- 12. Glibenclamide with hypoglycemia or hypoglycemia symptoms, previous problems with metformin, nonadherent  $\rightarrow$  stop medications, recheck A1c in 3 months
- 13. Metformin and glibenclamide without problems, adherent
  - a. Metformin 850 mg + glibenclamide 2.5-5 mg  $\rightarrow$  metformin 850 mg
  - b. Metformin 850 mg + glibenclamide 10 mg  $\rightarrow$  metformin 1700 mg
  - c. Metformin 1700-2550 mg + glibenclamide 2.5-5 mg  $\rightarrow$  metformin 1700 mg
- d. Metformin 1700-2550 mg + glibenclamide 10 mg  $\rightarrow$  metformin 1700 mg + glibenclamide 2.5 mg 14. Metformin and glibenclamide without problems, nonadherent

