#### [name]

- $\hbox{8. Glibenclamide without problems, previous problems with metformin, nonadherent } \\$ 
  - a. Willing to take metformin
    - i. Glibenclamide 2.5 mg  $\rightarrow$  metformin 850 mg
    - ii. Glibenclamide 5 mg  $\rightarrow$  metformin 850 mg + glibenclamide 2.5 mg
    - iii. Glibenclamide 10 mg  $\rightarrow$  metformin 850 mg + glibenclamide 5 mg
  - b. Refuses to take metformin
    - i. Glibenclamide 2.5 mg  $\rightarrow$  stop medications, recheck A1c in last 3 months
    - ii. Glibenclamide 5 mg  $\rightarrow$  glibenclamide 2.5 mg
    - iii. Glibenclamide 10 mg  $\rightarrow$  glibenclamide 5 mg
- 9. Glibenclamide with hypoglycemia or hypoglycemia symptoms, no previous problems with metformin, adherent  $\rightarrow$  same as #5
- 10. Glibenclamide with hypoglycemia or hypoglycemia symptoms, no previous problems with metformin, nonadherent  $\rightarrow$  same as #5
- 11. Glibenclamide with hypoglycemia or hypoglycemia symptoms, previous problems with metformin, adherent
  - a. Agrees to take metformin
    - i. Glibenclamide 2.5-5 mg  $\rightarrow$  metformin 850 mg
    - ii. Glibenclamide 10 mg  $\rightarrow$  metformin 850 mg + glibenclamide 2.5 mg
  - b. Refuses to take metformin
    - i. Glibenclamide 2.5 mg  $\rightarrow$  stop medications, recheck A1c in 3 months
    - ii. Glibenclamide 5 mg  $\rightarrow$  glibenclamide 2.5 mg
    - iii. Glibenclamide 10 mg  $\rightarrow$  glibenclamide 5 mg
- 12. Glibenclamide with hypoglycemia or hypoglycemia symptoms, previous problems with metformin, nonadherent → same as #11
- 13. Metformin and glibenclamide without problems, adherent  $\rightarrow$  continue current doses
- 14. Metformin and glibenclamide without problems, nonadherent
  - a. Metformin any dose + glibenclamide 2.5 mg  $\rightarrow$  metformin current dose
  - b. Metformin any dose + glibenclamide 5 mg  $\rightarrow$  metformin current dose + glibenclamide 2.5 mg
  - c. Metformin any dose + glibenclamide 10 mg  $\rightarrow$  metformin current dose + glibenclamide 5 mg
- 15. Metformin and glibenclamide, problems with metformin, adherent
  - a. Metformin 850 mg + glibenclamide any dose, agrees to take metformin →metformin 850 mg + current glibenclamide dose
  - b. Metformin 850 mg + glibenclamide any dose, refuses to take metformin → current glibenclamide dose
  - c. Metformin 1700 mg + glibenclamide any dose  $\rightarrow$  metformin 850 mg + current glibenclamide dose

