# Tx goal< A1c <9 AND FBG >130(150) OR PPBG >180(200

- 1. Metformin without problems, adherent
  - a. Metformin 850 mg  $\rightarrow$  metformin 1700 mg
  - b. Metformin 1700 mg  $\rightarrow$  metformin 2550 mg
  - c. Metformin 2550 mg  $\rightarrow$  metformin 2550 mg + glibenclamide 2.5 mg
- 2. Metformin without problems, nonadherent
  - a. Metformin 850 mg  $\rightarrow$  metformin 1700 mg
  - b. Metformin 1700 mg  $\rightarrow$  metformin 1700 mg
  - c. Metformin 2550 mg  $\rightarrow$  metformin 2550 mg
- 3. Metformin with problems, adherent
  - a. Metformin 850 mg, agrees to take metformin  $\rightarrow$  metformin 850 mg + glibenclamide 2.5 mg
  - b. Metformin 850 mg, refuses to take metformin  $\rightarrow$  glibenclamide 2.5 mg
  - c. Metformin 1700 mg  $\rightarrow$  metformin 850 mg + glibenclamide 2.5 mg
  - d. Metformin 2550 mg  $\rightarrow$  metformin 1700 mg + glibenclamide 2.5 mg
- 4. Metformin with problems, nonadherent  $\rightarrow$  same as #3
- 5. Glibenclamide without problems, no previous problems with metformin, adherent
  - a. Any dose  $\rightarrow$  metformin 1700 mg + glibenclamide current dose
- 6. Glibenclamide without problems, no previous problems with metformin, nonadherent

Version #: 1.0

[name]

- a. All doses  $\rightarrow$  metformin 1700 mg
- 7. Glibenclamide without problems, previous problems with metformin, adherent
  - Glibenclamide any dose, agrees to take metformin → metformin 850 mg + current glibenclamide dose
  - b. Refuses to take metformin
    - i. Glibenclamide 2.5 mg  $\rightarrow$  glibenclamide 5 mg
    - ii. Glibenclamide 5 mg  $\rightarrow$  glibenclamide 10 mg
    - iii. Glibenclamide 10 mg  $\rightarrow$  glibenclamide 10 mg
- 8. Glibenclamide without problems, previous problems with metformin, nonadherent
  - a. Willing to take metformin
    - i. Glibenclamide 2.5 mg  $\rightarrow$  metformin 850 mg
    - ii. Glibenclamide 5 mg  $\rightarrow$  metformin 850 mg + glibenclamide 2.5 mg
    - iii. Glibenclamide 10 mg  $\rightarrow$  metformin 850 mg + glibenclamide 5 mg
    - b. Refuses to take metformin  $\rightarrow$  continue current glibenclamide dose
- 9. Glibenclamide with hypoglycemia or hypoglycemia symptoms, no previous problems with metformin, adherent
  - a. Glibenclamide 2.5-5 mg  $\rightarrow$  metformin 1700 mg
  - b. Glibenclamide 10 mg  $\rightarrow$  metformin 1700 mg + glibenclamide 2.5 mg

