- 10. Glibenclamide with hypoglycemia or hypoglycemia symptoms, no previous problems with metformin, nonadherent → same as #9
- 11. Glibenclamide with hypoglycemia or hypoglycemia symptoms, previous problems with metformin, adherent
  - a. Agrees to take metformin
    - i. Glibenclamide 2.5 mg  $\rightarrow$  metformin 850 mg
    - ii. Glibenclamide 5 mg  $\rightarrow$  metformin 850 mg + glibenclamide 2.5 mg
    - iii. Glibenclamide 10 mg  $\rightarrow$  metformin 850 mg + glibenclamide 5 mg
  - b. Refuses to take metformin
    - i. Glibenclamide 2.5 mg  $\rightarrow$  MD consult
    - ii. Glibenclamide 5 mg  $\rightarrow$  glibenclamide 2.5 mg
    - iii. Glibenclamide 10 mg  $\rightarrow$  glibenclamide 5 mg
- 12. Glibenclamide with hypoglycemia or hypoglycemia symptoms, previous problems with metformin, nonadherent  $\rightarrow$  same as #11
- 13. Metformin and glibenclamide without problems, adherent
  - a. Metformin 850 mg + glibenclamide any dose → metformin 1700 mg + current glibenclamide dose
     b. Metformin 1700 mg + glibenclamide any dose → metformin 2550 mg + glibenclamide current dose
  - c. Metformin 2550 mg + glibenclamide 2.5 mg → metformin 2550 mg + glibenclamide 5 mg
  - d. Metformin 2550 mg + glibenclamide 5 mg  $\rightarrow$  metformin 2550 mg + glibenclamide 10 mg
  - e. Metformin 2550 mg + glibenclamide 10 mg → metformin 2550 mg + glibenclamide 10 mg
- 14. Metformin and glibenclamide without problems, nonadherent  $\rightarrow$  continue current doses
- 15. Metformin and glibenclamide, problems with metformin, adherent
  - a. Agrees to take metformin
    - i. Metformin 850 mg + glibenclamide 2.5 mg  $\rightarrow$  metformin 850 mg + glibenclamide 5 mg
    - ii. Metformin 850 mg + glibenclamide 5 mg  $\rightarrow$  metformin 850 mg + glibenclamide 10 mg
    - iii. Metformin 850 mg + glibenclamide 10 mg  $\rightarrow$  metformin 850 mg + glibenclamide 10 mg
    - b. Refuses to take metformin
      - i. Metformin 850 mg + glibenclamide 2.5 mg  $\rightarrow$  glibenclamide 5 mg

[name]

- ii. Metformin 850 mg + glibenclamide 5 mg  $\rightarrow$  glibenclamide 10 mg
- iii. Metformin 850 mg + glibenclamide 10 mg → glibenclamide 10 mg
- c. Metformin 1700 mg + glibenclamide 2.5 mg  $\rightarrow$  metformin 850 mg + glibenclamide 5 mg
- d. Metformin 1700 mg + glibenclamide 5 mg  $\rightarrow$  metformin 850 mg + glibenclamide 10 mg
- e. Metformin 1700 mg + glibenclamide 10 mg  $\rightarrow$  metformin 850 mg + glibenclamide 10 mg

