  - h. Metformin 2550 mg + glibenclamide 10 mg → metformin 1700 mg + glibenclamide 5 mg
- 20. Metformin and glibenclamide, problems with metformin, hypoglycemia or hypoglycemia symptoms, nonadherent → same as #19

9≤ A1c ≤14 AND [FBG ≤130(150) OR PPBG ≤180(200)]  $\rightarrow$  Use dosing recommendations for Tx goal< A1c <9

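### At A1c visits with A1c of 6 or more, Appendix 11 sets no lower fasting-glucose limit, so adherent patients on metformin plus glibenclamide can keep their full glibenclamide dose at a below-goal reading for which Appendix 10 would cut it

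*Combined protocol and SAP*

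**What the plan says.** Section 7.4.1 (Enrollment Visit) sets the fasting goal as a range: 80-130 mg/dL, or 90-150 for patients aged 65 or over or with at least two comorbidities. The postprandial goals have only an upper limit. Appendix 4 takes over when a reading is below 70.

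Section 7.4.2 (Month 3 Visit) says that when A1c is measured, Appendix 11 is used in place of Appendix 10. Every third monthly visit is such a visit. Appendix 10 has a separate band for fasting glucose below 80 (below 90 relaxed). Appendix 11 has no such band at A1c of 6 or more:

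- The table for A1c from 6 to goal carries no glucose condition.
- For A1c above goal but under 9 with glucose in range, the rule is "Tx goal< A1c <9 AND [FBG ≤130(150) OR PPBG ≤180(200)] → Use dosing recommendations for 6≤ A1c ≤Tx goal".
- For A1c 9 to 14 with glucose in range, the rule is "Use dosing recommendations for Tx goal< A1c <9".

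Both redirects state only an upper glucose limit. The only dosing table that matches the second redirect's target by name is headed "Tx goal< A1c <9 AND FBG >130(150" and so on, a condition that a patient with low fasting glucose does not meet.

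**The concern.** A fasting value of 70-79 (70-89 relaxed) is too high for the hypoglycemia protocol and too low for the protocol's own goal. At a monthly visit it triggers a glibenclamide cut. At an A1c visit nothing separates it from a value of, say, 110.

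Section 2.7.1 names glibenclamide as probably the most harmful drug in the program, and section 3 makes safety of titration a secondary objective. The wider gap, 70-89, falls on the older and sicker patients. The health worker acts on one recommendation from the app and dispenses before the physician reviews the visit. An incorrect app recommendation is also a primary safety endpoint (section 4.1.3), and while the 9-14 redirect is unclear there is no agreed correct answer for those patients.

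**Working it through.** The plan gives no figure to reproduce here, so the check compares the tables entry by entry.

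**One patient, three instructions.** Take an adherent patient on metformin 2550 mg plus glibenclamide 5 mg, with no symptoms, fasting glucose 75 and the standard goal.

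- Monthly visit: Appendix 10, low band, row 13c ("Metformin 1700-2550 mg + glibenclamide 5 mg") gives metformin 1700 mg plus glibenclamide 2.5 mg.
- A1c visit, A1c 6 to under 9: the at-goal table, row 13 ("13. Metformin and glibenclamide without problems, adherent") leaves both doses as they are, so glibenclamide stays at 5 mg.
- A1c visit, A1c 9 to 14, redirect read literally: the above-goal table, row 13d gives glibenclamide 10 mg. The row before it, 13c, reads "Metformin 2550 mg + glibenclamide 2.5 mg → metformin 2550 mg + glibenclamide 5 mg". If the redirect instead chains on to the at-goal table, the dose stays at 5 mg.

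**All adherent situations on glibenclamide.** Each regimen is crossed with glibenclamide 2.5, 5 and 10 mg. There are no hypoglycemia symptoms and fasting glucose is 70-79 (70-89). Entries are counts of what happens to glibenclamide.

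| Regimen | Situations | Appendix 10 low band: cut | At-goal table: unchanged / cut | Above-goal table: raised / unchanged |
|---|---|---|---|---|
| Glibenclamide alone, no metformin problem | 3 | 3 | 0 / 3 | 0 / 3 |
| Glibenclamide alone, past metformin problem, agrees to it | 3 | 3 | 0 / 3 | 0 / 3 |
| Glibenclamide alone, refuses metformin | 3 | 3 | 3 / 0 | 2 / 1 |
| Both drugs, no problem, metformin 850 or 1700 mg | 6 | 6 | 6 / 0 | 0 / 6 |
| Both drugs, no problem, metformin 2550 mg | 3 | 3 | 3 / 0 | 2 / 1 |
| Both drugs, metformin problem (850 agrees, 850 refuses, 1700, 2550) | 12 | 12 | 12 / 0 | 8 / 4 |
| Total | 30 | 30 | 24 / 6 | 12 / 18 |

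Where yesterday's dose was taken, the at-goal table gives more glibenclamide than Appendix 10 in 26 of 30 (2.5 mg more in 17, 5 mg in 8, 10 mg in 1) and the same in 4.

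**Nonadherent situations.** The at-goal table cuts glibenclamide in 30 of 30. Over both groups it is unchanged in 24 of 60 and cut in 36. The above-goal table raises it in none of the 30 nonadherent situations.

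**Adherent, metformin only (7 situations).** The above-goal table starts glibenclamide in 5: row 1c ("metformin 2550 mg + glibenclamide 2.5 mg") and rows 3a to 3d. Appendix 10 starts it in none. The at-goal table starts it in 1: row 3b, metformin 850 mg refused.

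**Below A1c 6 the direction reverses.** At A1c 5 to under 6, a patient on "Metformin 1700-2550 mg + glibenclamide 2.5-5 mg" goes to metformin alone. Against Appendix 10, in the 30 adherent situations with yesterday's dose taken, that table gives less glibenclamide in 13, the same in 17 and more in none. There is no concern there.

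**The case against.** **Letting A1c lead is a stated choice.** Section 2.1 calls A1c the more definitive measure. Section 7.4.2 brings in current glucose so that a lagging A1c does not force a dose increase. Appendix 10's low band is not a pure safety limit either, because it also cuts glibenclamide at postprandial readings that are within goal. This stands in part. When A1c is above goal, cutting a drug on one reading of 70 or more is a clinical trade-off, so the Appendix 10 dose cannot be called the correct one there. But neither section says to disregard a reading below the fasting range.

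**Adherence.** A reader might infer that glibenclamide is mostly continued whatever the adherence. The tables do not support that, since every nonadherent at-goal row cuts it. Those cuts are sometimes smaller than Appendix 10's: more glibenclamide remains in 22 of 60 nonadherent situations, counting yesterday's dose taken or not.

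**Raised doses.** A reader might also infer that the protocol raises glibenclamide on low readings. That needs the literal reading of the 9-14 redirect, and on that reading an in-range fasting value of 80-130 leads to the same increase. The cause is the unclear redirect, not the missing lower limit alone.

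**Mitigation.** Physician review within a week, telephone advice, hypoglycemia teaching, cuts for reported symptoms and the next monthly visit all reduce the risk. This stands. Review and the next visit come after dispensing, however, and Appendix 11 prompts no call for such a reading.

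**Conclusion.** The gap is real but bounded. It concerns A1c visits (2 of the 6 guaranteed monthly visits, 4 of 12 if followed to a year), A1c of 6 or more, a fasting reading of 70-79 (70-89 relaxed) and no hypoglycemia symptoms.

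At A1c 6 to under 9, the full glibenclamide dose continues in adherent patients on both drugs and in adherent glibenclamide-only patients who refuse metformin: 24 of 30 adherent situations, all of which Appendix 10 cuts or stops. At A1c 9 to 14, the result depends on a redirect the text does not settle: 12 of 30 raised if literal, none if chained.

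The counts weight every table entry equally. The documents do not say how often such readings occur, so nothing here is a rate of harm. Readings below 70 go to Appendix 4, and A1c above 14 goes to consultation; the point covers neither. It should be corrected, but it does not show that the algorithm as a whole is unsafe.

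**What to change.** 1. State which table the A1c 9-14 redirect means.
2. Add a guard to Appendix 11: at A1c of 6 or more with fasting glucose below 80 (below 90 relaxed), never start or raise glibenclamide at that visit. This includes row 3b of the at-goal table. A patient who would be left with no diabetes drug goes to the medical director.
3. For patients already on glibenclamide with A1c from 6 to goal, apply the matching Appendix 10 low-band row, and send any case that leaves no drug to the medical director.
4. With A1c above goal, up to 14, prompt a call to the coordinator or medical director before dispensing rather than an automatic cut. This respects the dual-therapy rule at A1c of 9 or more in section 2.6.
5. Leave the rules for A1c below 6, postprandial readings and hypoglycemia unchanged.

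Cost: some extra calls, minor app reprogramming and retesting of the affected branches; no new data, visits or patients. The clinical price of step 3 is that glibenclamide is cut on one reading. Crossing the 30 situations with adherent or not, and yesterday's dose taken or not, gives 30 × 2 × 2 = 120. Over these the Appendix 10 rows stop glibenclamide in 90 (at-goal table: 32) and would leave no drug in 16 (at-goal table: 4); those 16 are the ones sent to the medical director. They also put metformin below the at-goal dose in 12 of the 120, where 2550 mg becomes 1700 mg.

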#### [name]

- i. Glibenclamide 2.5 mg  $\rightarrow$  MD consult
- ii. Glibenclamide 5 mg  $\rightarrow$  glibenclamide 2.5 mg
- iii. Glibenclamide 10 mg  $\rightarrow$  glibenclamide 5 mg
- 12. Glibenclamide with hypoglycemia or hypoglycemia symptoms, previous problems with metformin, nonadherent → same as #11
- 13. Metformin and glibenclamide without problems, adherent
  - a. Metformin 850 mg + glibenclamide any dose → metformin 1700 mg + current glibenclamide dose
     b. Metformin 1700 mg + glibenclamide any dose → metformin 2550 mg + glibenclamide current dose
  - c. Metformin 2550 mg + glibenclamide 2.5 mg  $\rightarrow$  metformin 2550 mg + glibenclamide 5 mg
  - d. Metformin 2550 mg + glibenclamide 5 mg  $\rightarrow$  metformin 2550 mg + glibenclamide 10 mg
  - e. Metformin 2550 mg + glibenclamide 10 mg → metformin 2550 mg + glibenclamide 10 mg
- 14. Metformin and glibenclamide without problems, nonadherent  $\rightarrow$  continue current doses
- 15. Metformin and glibenclamide, problems with metformin, adherent
  - a. Agrees to take metformin
    - i. Metformin 850 mg + glibenclamide 2.5 mg → metformin 850 mg + glibenclamide 5 mg
    - ii. Metformin 850 mg + glibenclamide 5 mg → metformin 850 mg + glibenclamide 10 mg
    - iii. Metformin 850 mg + glibenclamide 10 mg  $\rightarrow$  metformin 850 mg + glibenclamide 10 mg
    - b. Refuses to take metformin
      - i. Metformin 850 mg + glibenclamide 2.5 mg  $\rightarrow$  glibenclamide 5 mg
      - ii. Metformin 850 mg + glibenclamide 5 mg  $\rightarrow$  glibenclamide 10 mg
      - iii. Metformin 850 mg + glibenclamide 10 mg  $\rightarrow$  glibenclamide 10, mg
    - c. Metformin 1700 mg + glibenclamide 2.5 mg  $\rightarrow$  metformin 850 mg + glibenclamide 5 mg
    - d. Metformin 1700 mg + glibenclamide 5 mg  $\rightarrow$  metformin 850 mg + glibenclamide 10 mg
    - e. Metformin 1700 mg + glibenclamide 10 mg  $\rightarrow$  metformin 850 mg + glibenclamide 10
    - f. Metformin 2550 mg + glibenclamide 2.5 mg  $\rightarrow$  metformin 1700 mg + glibenclamide 5 mg
    - g. Metformin 2550 mg + glibenclamide 5 mg  $\rightarrow$  metformin 1700 mg + glibenclamide 10 mg
  - h. Metformin 2550 mg + glibenclamide 10 mg → metformin 1700 mg + glibenclamide 10 mg

16. Metformin and glibenclamide, problems with metformin, nonadherent

- Metformin 850 mg + glibenclamide any dose, agrees to take metformin → metformin 850 mg + current glibenclamide dose
- b. Metformin 850 mg + glibenclamide any dose, refuses to take metformin → current glibenclamide dose
- c. Metformin 1700 mg + glibenclamide any dose  $\rightarrow$  metformin 850 mg + current glibenclamide dose
- d. Metformin 2550 mg + glibenclamide any dose → metformin 1700 mg + current glibenclamide dose

17. Metformin and glibenclamide, hypoglycemia or hypoglycemia symptoms, adherent

- a. Metformin 850 mg + glibenclamide 2.5 mg  $\rightarrow$  metformin 1700 mg
- b. Metformin 850 mg + glibenclamide 5 mg → metformin 1700 mg + glibenclamide 2.5 mg
- c. Metformin 850 mg + glibenclamide 10 mg  $\rightarrow$  metformin 1700 mg + glibenclamide 5 mg
- d. Metformin 1700 mg + glibenclamide 2.5 mg → metformin 2550 mg
- e. Metformin 1700 mg + glibenclamide 5 mg  $\rightarrow$  metformin 2550 mg + glibenclamide 2.5 mg
- f. Metformin 1700 mg + glibenclamide 10 mg → metformin 2550 mg + glibenclamide 5 mg
- g. Metformin 2550 mg + glibenclamide 2.5 mg  $\rightarrow$  metformin 2550 mg
- h. Metformin 2550 mg + glibenclamide 5 mg → metformin 2550 mg + glibenclamide 2.5 mg
- i. Metformin 2550 mg + glibenclamide 10 mg  $\rightarrow$  metformin 2550 mg + glibenclamide 5 mg

18. Metformin and glibenclamide, hypoglycemia or hypoglycemia symptoms, nonadherent  $\rightarrow$  same as #17

Version #: 1.0

[name]

- 19. Metformin and glibenclamide, problems with metformin, hypoglycemia or hypoglycemia symptoms, adherent
  - a. Agrees to take metformin
    - i. Metformin 850 mg + glibenclamide 2.5 mg  $\rightarrow$  metformin 850 mg
    - ii. Metformin 850 mg + glibenclamide 5 mg  $\rightarrow$  metformin 850 mg + glibenclamide 2.5 mg
    - iii. Metformin 850 mg + glibenclamide 10 mg  $\rightarrow$  metformin 850 mg + glibenclamide 5 mg
  - b. Refuses to take metformin
    - i. Metformin 850 mg + glibenclamide 2.5 mg  $\rightarrow$  MD consult
    - ii. Metformin 850 mg + glibenclamide 5 mg  $\rightarrow$  glibenclamide 2.5 mg
    - iii. Metformin 850 mg + glibenclamide 10 mg  $\rightarrow$  glibenclamide 5 mg
  - c. Metformin 1700 mg + glibenclamide 2.5 mg  $\rightarrow$  metformin 850 mg
  - d. Metformin 1700 mg + glibenclamide 5 mg  $\rightarrow$  metformin 850 mg + glibenclamide 2.5 mg
  - e. Metformin 1700 mg + glibenclamide 10 mg  $\rightarrow$  metformin 850 mg + glibenclamide 5 mg
  - f. Metformin 2550 mg + glibenclamide 2.5 mg  $\rightarrow$  metformin 1700 mg
  - g. Metformin 2550 mg + glibenclamide 5 mg  $\rightarrow$  metformin 1700 mg + glibenclamide 2.5 mg
  - h. Metformin 2550 mg + glibenclamide 10 mg → metformin 1700 mg + glibenclamide 5 mg
- 20. Metformin and glibenclamide, problems with metformin, hypoglycemia or hypoglycemia symptoms, nonadherent → same as #19

9≤ A1c ≤14 AND [FBG ≤130(150) OR PPBG ≤180(200)]  $\rightarrow$  Use dosing recommendations for Tx goal< A1c <9

